11. STATISTICS

No formal sample size calculation was done as this is an open-label extension trial. Up to 90 subjects will be included.

Data will be summarised using summary statistics. Continuous data will be presented with the number of observations, mean value, standard deviation, minimum, quartile 1, median, quartile 3 and maximum value. Categorical data will be presented as counts and percentages. The data will be presented by visit in tables and graphs. Individual subject data will be listed. Further details of all analyses will be given in the statistical analysis plan.

No “analysis sets” (intention to treat, per protocol, etc.) are defined. All subjects will be included in the analyses/data presentations (equivalent to a Full Analysis Set).

Only recorded data will be analysed/presented and any subjects who have missing data will only have observed data reported, with no imputation for missing data.

Interim cuts of data may be done on a yearly basis and as needed for regulatory purposes (e.g. 120-day safety update).

Data listings will show all recorded data.

Data from the trial is planned to be combined with relevant data from the IMPALA trial; these combined analyses will be reported separately.

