APPENDIX 4.2 TRIAL SPECIFIC GUIDELINE FOR THE 6MWT 6 MWT AND CR10 (BORG'S) DYSPNOEA SCALE

6MWT

The 6MWT should be conducted according to ATS/ERS technical standard (Field Walking Tests in Chronic Respiratory Disease – Eur Respir J 2014; 44:1428-1446).

The 6MWT should be performed on a flat, straight course with a hard surface with little pedestrian traffic

The walking course should be 30 m or more in length.

The end of the course should be marked such that they are easily visible to patients. The same course should be used at each visit.

The patient should sit at rest in a chair, located near the starting position, for at least 10 minutes before the test starts

The test should be completed with the subject breathing room air, if possible. If a patient is on chronic oxygen therapy and not able to complete the 6MWT on room air, an oxygen titration procedure will be conducted at screening. The procedure described in Appendix 4 should be followed. The same flow of oxygen should then be used at the subject's subsequent tests in the trial, unless a higher flow is required due to the subject's medical condition.

Patients should be encouraged every 60 seconds using standard phrases. Other words of encouragement and other nonverbal prompts should not be used.

If the patient stops walking during the test, the timer must not be stopped. The patient should be allowed to rest while sitting or standing, as they prefer. During the stop, standard encouragement should be given every 30 seconds. The time the patient stopped during the test, should be noted in the eCRF.

If SpO₂ is < 80% then the test should be stopped

Two 6MWTs should be performed (due to the learning effect on the test), and the result from the test with the longest distance walked should be recorded. If the subject is not able to complete more than one test due to exhaustion or adverse events, this should be noted on the worksheet. There must be at least 30 minutes between the two tests.

The total distance walked should be recorded

SpO₂ should be measured using a pulse oximeter continuously during the test. The start value and the lowest value during 6MWT should be recorded

Start heart rate and end heart rate should also be recorded

Use the study-specific worksheet for documenting values, which is provided by sponsor to the sites.

The results from the 6MWT with the longest distance walked and the related SpO₂ and CR10 (Borg) scale results should be entered in the eCRF.

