Standard encouragement during a 6-minute walk test

1 min: You are doing well. You have 5 minutes to go.

2 min: Keep up the good work. You have 4 minutes to go.

3 min: You are doing well. You are halfway.

4 min: Keep up the good work. You have only 2 minutes left.

5 min: You are doing well. You have only 1 minute to go.

6 min: Please stop where you are.

If the patient stops during the test, every 30 s once SpO₂ is $\geq 85\%$ the following standard phrase should be use:

“Please resume walking whenever you feel able.”

CR10 Scale/Borg’s dyspnoea scale

The CR10 (Borg’s) scale for dyspnoea provided by Savara should be rated before and after the 6MWT. Let the patient read the instruction before rating their dyspnoea on the CR10 scale. Standard instructions for the CR10 (Borg scale) will be provided in local language.

If possible, the test should be conducted using the same oxygen flow level as was used in IMPALA. If a subject has started chronic oxygen therapy after being enrolled in IMPALA, an oxygen titration procedure should be conducted as described below.

This procedure only applies for patients on chronic oxygen supplementation at screening:

The patient will perform an O₂ titration procedure at Screening to determine the amount of supplemental oxygen that the patient needs to complete the 6MWT without developing O₂ desaturation. This oxygen flow rate will represent the patient’s baseline O₂ flow rate for all subsequent 6MWT procedures for this study.

Equipment and supplies:

The equipment and supplies needed for the Oxygen Titration Procedure are the same as those needed for the 6MWT. Verify that your oxygen flow meter is accurate (to within 0.5 liters per minute).

Patient safety:

The safety precautions for the Oxygen titration procedure at the screening visit are same as required for the 6MWT.

Procedure:

Step 1: Resting O₂ Titration

Attach the pulse oximeter. Set it to alarm when SpO₂ falls below 83%.

Instruct the patient to sit still and not chat.

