Discontinue supplemental oxygen. Start the timer for 10 min. If resting SpO₂ decreases to below 83% during the 10 minutes resting period, then start supplemental oxygen at 2 L/min. If resting SpO₂ again decreases below 83% during the next 10 minutes, then increase O₂ to 4 L/min. If resting SpO₂ remains below 83% during the next 10 minutes, then increase OR2R to 6 L/min. If resting SpO₂ remains below 83% during the 10 minutes at rest on 6 L/min of supplemental oxygen, the patient should not conduct the 6MWT.

The lowest oxygen flow for which a patient can maintain a resting SpO₂ >83% for 10 minutes will be the initial flow rate for the Walking portion of the O₂ titration procedure.

Step 2: Walking O₂ Titration

Before starting the exercise evaluation, the patient should be seated and resting for at least 10 minutes on the oxygen flow rate determined during the resting O₂ titration procedure.

Follow the 6MWT procedures, starting at the O₂ flow rate established in the resting O₂ titration. Start the timer when the patient begins walking.

If the patient's SpO₂ decreases to below 83%, stop the walk and increase supplemental oxygen by 2 L/min. The patient should then be seated and allowed to rest for 5 min. The Walking O₂ titration procedure should then be repeated at the higher O₂ flow rate. If the patient's SpO₂ decreases to below 83% at any time, repeat the Walking titration. If during the 6MWT on 6 L/min of oxygen SpO₂ drops below 83% (sustained for at least 30 seconds), stop the walk. If the patient has not completed a distance of >150 meters, the patient should not conduct the 6MWT

The lowest oxygen flow on which a patient can complete the 6MWT without developing a SpO₂ below 83% will be the patient's O₂ flow for all subsequent 6MWT conducted during the course of the study.

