7.2.1 Blood Gas Analysis

The following variables will be assessed from an arterial blood gas sample collected at the timepoints shown in Table 1.

- PaO₂ (mmHg) – arterial partial pressure of oxygen
- PaCO₂ (mmHg) – arterial partial pressure of carbon dioxide
- F_iO₂ – fraction of inspired oxygen

P_{atm} (ambient atmospheric pressure) must be collected using a bedside barometer. The P_{H₂O} (saturated vapor pressure of water at body temperature) will be set to 47 mmHg / 6.266 kPa.

The Aa Gradient (A-a)DO₂ will be calculated centrally using the following formula:

$$Aa\ Gradient = \left(F_i O_2 (P_{atm} - P_{H_2O}) - \frac{P_a CO_2}{0.8} \right) - P_a O_2$$

The Aa Gradient will be summarized by visit. A corresponding mean and with confidence interval (CI) plot over time will be provided. Subjects on supplementary oxygen during blood gas sample are excluded from the relevant visits in the summary.

A corresponding listing by subject and visit will be provided including all subjects regardless of use of supplemental oxygen.

Any Aa Gradients reported in kPa will be converted to a result in mmHg, this will be done using a factor $k=7.5$ ($kPa \times 7.5 = mmHg$).

7.2.2 6-minute Walk Test (6MWT)

Exercise capacity will be assessed using the 6MWT to measure the 6-minute walk distance (6MWD) at the timepoints shown in Table 1.

The 6MWT should be performed twice at each visit in accordance with the European Respiratory Society (ERS)/American Thoracic Society (ATS) guidance.

Data from both tests should be entered in the eCRF. Parameters to be recorded comprise pre and post walk dyspnea score using the Borg (CR-10) Dyspnea Score (including the difference post minus pre dyspnoea score), SpO₂ (%) at start, worst SpO₂ (%) during the walk, distance walked (m), duration of the walk (minutes and seconds), oxygen flow rate if applicable, reason for stopping early (if applicable). For each subject and each visit the results from the test with the longest distance walked will be used in the reporting of the trial.

Distance in meter, Borg score endpoints, and SpO₂ and the desaturation (first SpO₂-worst SpO₂) will be summarized by treatment and visit. Furthermore, number of subjects (N, %) who completed the test will be presented by treatment and visit.

A corresponding mean and CI plot over time as well as a corresponding listing by subject and visit will be provided for each of the endpoints.

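### Subjects barred from the 6-minute walk after a failed oxygen titration have no place in the 6MWD summaries, and the protocol is unclear about when that bar applies

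*Protocol*

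**What the plan says.** **The bar.** Protocol Appendix 4.2 describes an oxygen titration in two steps, and either can exclude a subject from the 6MWT.
- Step 1, at rest. If SpO₂ stays under 83% "at rest on 6 L/min of supplemental oxygen, the patient should not conduct the 6MWT".
- Step 2, walking. The walk on 6 L/min is stopped for a sustained SpO₂ under 83%. Then: "If the patient has not completed a distance of >150 meters, the patient should not conduct the 6MWT".

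**When titration applies.** The main 6MWT text says that, for a subject on chronic oxygen who cannot complete the test on room air, "an oxygen titration procedure will be conducted at screening". Later the appendix says: "If a subject has started chronic oxygen therapy after being enrolled in IMPALA, an oxygen titration procedure should be conducted as described below". The sentence immediately after that reads: "This procedure only applies for patients on chronic oxygen supplementation at screening".

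**An ordinary 6MWT.** "If SpO₂ is < 80% then the test should be stopped". The distance covered is still to be recorded, and a higher oxygen flow is allowed if the subject's condition requires it.

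**Analysis.** Protocol section 11 says "Only recorded data will be analysed/presented". SAP sections 4 and 7.4 agree and impute nothing. SAP section 7.2.2 uses the longer walk at each visit and adds that the "number of subjects (N, %) who completed the test will be presented by treatment and visit" (Table 14.2.2.13). No section gives a value or a category to a subject who was not permitted to walk.

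**The concern.** The bar is triggered by poor oxygenation or by a very short walk. These are close to what 6MWD is meant to measure, so any value missing for this reason is missing because of the outcome. Two subjects who perform equally badly can be treated differently: one whose ordinary 6MWT is stopped early contributes a low distance, and one who fails the titration contributes nothing.

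SAP section 5.2 lists 6MWD among the key secondary endpoints, and exercise capacity on long-term treatment is a stated objective. If barred subjects are left out unseen, the visit mean and the mean change from baseline are too high, and a statement that exercise capacity was maintained would rest partly on who was allowed to walk.

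**Working it through.** **Step 1: who can be lost, and when.** Three cases follow from the text.

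1. *A subject already on a set oxygen flow who worsens later.* No repeat titration is stated. The flow may be raised, the 6MWT goes ahead, it is stopped below 80%, and the distance is recorded. This subject stays in the mean with a low value.
2. *A subject titrated at Visit 1 who fails.* There is no Visit 1 distance. SAP section 5.1 fills a missing baseline with the nearest IMPALA value, so the subject can appear in the baseline summary with an earlier distance and supply nothing afterwards while the bar stands. Appendix 4.2 does not say whether or when a barred subject is retested.
3. *A subject who starts chronic oxygen during this trial.* The sentence on oxygen started after IMPALA enrolment has no end date and can be read to require titration here, so failure removes the subject after baseline. Under the sentence limiting titration to screening there is none, and case 1 applies.

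The screening limit cannot be applied literally. The flow chart (Protocol Table 1, repeated in the SAP) begins at Baseline, Visit 1, and has no screening visit. Oxygen started after baseline is foreseen: SAP section 7.2.7 has a summary category for it.

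**Step 2: what the planned outputs would show.** Table 14.2.2.13 gives the number and percentage completing, with no stated denominator. The 6MWT listing gives reasons for stopping early, not for never starting. SAP section 5.1 shows missing counts where relevant, without reason. The only planned table of missed assessments by cause concerns COVID-19 (SAP section 5.2).

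**Step 3: size.** The documents give no 6MWD mean or SD, no sample size calculation and no number barred, so there is no figure to reproduce. What follows is an illustration.

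From the documents: N = 60 enrolled (SAP section 3.2). Assumed: observed mean m, number barred k, distance d that barred subjects would have walked, and their baseline b.

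*Visit mean.* The all-subject mean is [(N − k)m + kd]/N, so the observed-only mean exceeds it by (k/N)(m − d).
- m = 450 m, k = 1, d = 150 m: (450 − 150)/60 = 5.0 m.
- m = 450 m, k = 1, d = 0 m: 450/60 = 7.5 m.
- m from 350 to 500 m, k = 1: from (350 − 150)/60 = 3.3 m to 500/60 = 8.3 m. For k = 3: 10.0 to 25.0 m.

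*Mean change from baseline.* With an assumed observed mean change of 0, the excess is (k/N)(b − d).
- b from 250 to 350 m, k = 1: from (250 − 150)/60 = 1.7 m to 350/60 = 5.8 m. For k = 3: 5.0 to 17.5 m.

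*By IMPALA treatment group.* SAP section 5.1 splits every table into three groups, but group sizes are not given. If a group had 20 subjects (60/3, assumed equal), one barred subject with m = 450 m would shift that group's visit mean by 300/20 = 15 m to 450/20 = 22.5 m.

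With k = 0 every shift is zero.

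**The case against.** The strongest reply is that titration is a one-time entry procedure. Both the main 6MWT text and the limiting sentence place it at screening, and its purpose is to fix the flow for later tests. On that reading a subject who fails is absent from the start and does not leave the mean after deteriorating, and later worsening is handled by the ordinary 6MWT, which keeps the short distance. This largely stands for subjects already on a set flow. It does not settle the matter, because the trial has no screening visit and the sentence on oxygen started after IMPALA enrolment carries no such limit. Nor does it remove case 2, in which an IMPALA distance serves as baseline with nothing after it.

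A second reply is that a gap would be visible by comparing Table 14.1.2 (subjects by visit) with the number of 6MWD values, and that decline would also appear in worst SpO₂, the disease severity score, aPAP status and oxygen use. That is partly right, but none of these outputs says why a 6MWD is absent.

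Third, 6MWD is only described and no hypothesis is tested (SAP section 7.5). This limits the consequence but does not remove the bias from the description.

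A reader might also infer that subjects on oxygen are treated differently from subjects on room air. The documents do not say so. The 80% stopping rule covers every ordinary 6MWT, with or without oxygen; the difference lies between a failed titration and an ordinary 6MWT.

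**Conclusion.** The gap is real but narrow. A subject barred under Appendix 4.2 has no 6MWD, the analysis gives that subject no value and no category, and the omission favours 6MWD whenever barred subjects would have walked less than the observed mean or, for change, declined more than the observed mean change. The documents conflict on whether titration, and with it the bar, can apply after entry.

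It is tempting to conclude that the subjects who worsen most drop out of the 6MWD mean and that exercise capacity will therefore look better. The documents do not support this. Most routes to later worsening keep the subject in the mean, on-trial loss depends on one undated sentence, and the number barred is unknown and may be zero.

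Under the assumptions shown, each barred subject of 60 adds about 3 to 8 m to the visit mean (5.0 to 7.5 m at an assumed mean of 450 m) and about 2 to 6 m to the mean change. This is a potential bias that is cheap to guard against, not a demonstrated one.

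**What to change.** 1. **Protocol Appendix 4.2.** Reconcile the screening-only wording with the sentence on oxygen started after IMPALA enrolment, and state at which visit or visits of this trial the titration applies. The SpO₂, flow and distance thresholds are clinical matters and are outside this point.
2. **SAP section 7.2.2 and Table 14.2.2.13.** Use subjects attending the visit as the denominator, with four rows: completed; stopped early; not permitted to walk under Appendix 4.2; not done for other reasons.
3. **One supplementary 6MWD summary**, beside the observed-data one. Give the median value and median change from baseline by visit, with barred subject-visits ranked worst. A median needs only the rank, so no distance has to be invented. Label it a sensitivity summary, since it departs from the recorded-data-only rule.

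Titration-walk distances should not stand in for 6MWD. A repeat titration walk may follow only 5 minutes of rest, whereas two 6MWTs must be at least 30 minutes apart.

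**Cost.** Extra rows in an existing table, one more summary, and possibly a slightly less favourable 6MWD result. SAP version 3.0 is dated 21 January 2021 and treatment was to run only to the end of 2020, so the reason for a missing walk may have to be obtained from sites retrospectively. Where it cannot be recovered, the table should say so. If nobody was barred, the new row shows zero and this question about the 6MWD result is closed.

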APPENDIX 4.3 ST GEORGE'S RESPIRATORY QUESTIONNAIRE

ST. GEORGE'S RESPIRATORY QUESTIONNAIRE ORIGINAL ENGLISH VERSION

ST. GEORGE'S RESPIRATORY QUESTIONNAIRE (SGRQ)

This questionnaire is designed to help us learn much more about how your breathing is troubling you and how it affects your life. We are using it to find out which aspects of your illness cause you most problems, rather than what the doctors and nurses think your problems are.

Please read the instructions carefully and ask if you do not understand anything. Do not spend too long deciding about your answers.

Before completing the rest of the questionnaire:

Please tick in one box to show how you describe your current health:

Very good Good Fair Poor Very poor

Copyright reserved
P.W. Jones, PhD FRCP
Professor of Respiratory Medicine,
St. George's University of London,
[name],
[name],
[name].

[contact]
[contact]

UK/ English (original) version

1

continued...

E:\institute\cubadea\project\gsk1881\questionnaire\original\english\grq.doc 14/03/03

St. George's Respiratory Questionnaire
PART 1

Questions about how much chest trouble you have had over the past 4 weeks.

Please tick (✓) one box for each question:

	most days a week	several days a week	a few days a month	only with chest infections	not at all
1. Over the past 4 weeks, I have coughed:					
2. Over the past 4 weeks, I have brought up phlegm (sputum):					
3. Over the past 4 weeks, I have had shortness of breath:					
4. Over the past 4 weeks, I have had attacks of wheezing:					
5. During the past 4 weeks, how many severe or very unpleasant attacks of chest trouble have you had?	Please tick (✓) one:				
	more than 3 attacks 				
	3 attacks 				
	2 attacks 				
	1 attack 				
	no attacks 				
6. How long did the worst attack of chest trouble last? (Go to question 7 if you had no severe attacks)	Please tick (✓) one:				
	a week or more 				
	3 or more days 				
	1 or 2 days 				
	less than a day 				
7. Over the past 4 weeks, in an average week, how many good days (with little chest trouble) have you had?	Please tick (✓) one:				
	No good days 				
	1 or 2 good days 				
	3 or 4 good days 				
	nearly every day is good 				
	every day is good 				
8. If you have a wheeze, is it worse in the morning?	Please tick (✓) one:				
	No 				
	Yes 				

**St. George's Respiratory Questionnaire
PART 2**

Section 1	
How would you describe your chest condition?	
	Please tick (✓) one:
The most important problem I have	
Causes me quite a lot of problems	
Causes me a few problems	
Causes no problem	
If you have ever had paid employment.	
	Please tick (✓) one:
My chest trouble made me stop work altogether	
My chest trouble interferes with my work or made me change my work	
My chest trouble does not affect my work	
Section 2	
Questions about what activities usually make you feel breathless these days.	
	Please tick (✓) in each box that applies to you these days :
	True False
Sitting or lying still	 
Getting washed or dressed	 
Walking around the home	 
Walking outside on the level	 
Walking up a flight of stairs	 
Walking up hills	 
Playing sports or games	 

St. George's Respiratory Questionnaire PART 2

Section 3

Some more questions about your cough and breathlessness these days.

Please tick (✓) in *each box* that applies to you *these days*:

	True	False
My cough hurts		
My cough makes me tired		
I am breathless when I talk		
I am breathless when I bend over		
My cough or breathing disturbs my sleep		
I get exhausted easily		

Section 4

Questions about other effects that your chest trouble may have on you these days.

Please tick (✓) in *each box* that applies to you *these days*:

	True	False
My cough or breathing is embarrassing in public		
My chest trouble is a nuisance to my family, friends or neighbours		
I get afraid or panic when I cannot get my breath		
I feel that I am not in control of my chest problem		
I do not expect my chest to get any better		
I have become frail or an invalid because of my chest		
Exercise is not safe for me		
Everything seems too much of an effort		

Section 5

Questions about your medication, if you are receiving no medication go straight to section 6.

Please tick (✓) in *each box* that applies to you *these days*:

	True	False
My medication does not help me very much		
I get embarrassed using my medication in public		
I have unpleasant side effects from my medication		
My medication interferes with my life a lot		

St. George's Respiratory Questionnaire PART 2

Section 6		
These are questions about how your activities might be affected by your breathing.		
Please tick (✓) in each box that applies to you because of your breathing :		
	True	False
I take a long time to get washed or dressed		
I cannot take a bath or shower, or I take a long time		
I walk slower than other people, or I stop for rests		
Jobs such as housework take a long time, or I have to stop for rests		
If I walk up one flight of stairs, I have to go slowly or stop		
If I hurry or walk fast, I have to stop or slow down		
My breathing makes it difficult to do things such as walk up hills, carrying things up stairs, light gardening such as weeding, dance, play bowls or play golf		
My breathing makes it difficult to do things such as carry heavy loads, dig the garden or shovel snow, jog or walk at 5 miles per hour, play tennis or swim		
My breathing makes it difficult to do things such as very heavy manual work, run, cycle, swim fast or play competitive sports		
 Section 7		
We would like to know how your chest usually affects your daily life.		
Please tick (✓) in each box that applies to you because of your chest trouble :		
	True	False
I cannot play sports or games		
I cannot go out for entertainment or recreation		
I cannot go out of the house to do the shopping		
I cannot do housework		
I cannot move far from my bed or chair		

St. George's Respiratory Questionnaire

Here is a list of other activities that your chest trouble may prevent you doing. (You do not have to tick these, they are just to remind you of ways in which your breathlessness may affect you):

- Going for walks or walking the dog
- Doing things at home or in the garden
- Sexual intercourse
- Going out to church, pub, club or place of entertainment
- Going out in bad weather or into smoky rooms
- Visiting family or friends or playing with children

Please write in any other important activities that your chest trouble may stop you doing:

.....
.....
.....
.....

Now would you tick in the box (one only) which you think best describes how your chest affects you:

- It does not stop me doing anything I would like to do
- It stops me doing one or two things I would like to do
- It stops me doing most of the things I would like to do
- It stops me doing everything I would like to do

Thank you for filling in this questionnaire. Before you finish would you please check to see that you have answered all the questions.
